10.3. Statistical Analyses

10.3.1. General Statistical Considerations

Statistical analysis of this study will be the responsibility of Lilly or its designee. A detailed statistical analysis plan (SAP) describing the statistical methodologies will be developed.

Efficacy analyses will be conducted on the Efficacy Analysis Set; safety analyses will be conducted on the Safety Analysis Set.

Descriptive statistics will include the number of patients, mean, standard deviation, median, minimum, and maximum for continuous measures, and frequency counts and percentages for categorical measures.

Investigators with fewer than 2 randomized patients per treatment group will be pooled for statistical analysis purposes. Sensitivity analyses accounting for missing data will be described in the SAP.

Unless otherwise noted, treatment comparisons of discrete variables will be made using logistic regression analysis with treatment and randomization stratification variables in the model. The percentages, difference in percentages, and 95% confidence interval (CI) of the difference in percentages will be reported.

Unless otherwise noted, treatment comparisons of continuous variables will be made using a restricted maximum likelihood-based mixed-effects model of repeated measures (MMRM). The model will include treatment, age group, and site, and, if applicable, study day and treatment-by-study day interaction as fixed categorical effects. Additional details on the MMRM analyses will be described in the SAP.

All tests of treatment effects will be conducted at a 1-sided alpha level of 0.05, unless otherwise stated.

Any change to the data analysis methods described in the protocol will require an amendment ONLY if it changes a principal feature of the protocol. Any other change to the data analysis methods described in the protocol, and the justification for making the change, will be described in the clinical study report (CSR). Additional exploratory analyses of the data will be conducted as deemed appropriate.

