10.3.3.3. Exploratory Analyses

Pulmonary function will be analyzed via MMRM analysis.

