Unless otherwise noted, treatment comparisons of quantitative variables will be made using a restricted maximum likelihood-based mixed-effects model of repeated measures (MMRM). The model will include treatment, age group, sex, and site as fixed categorical effects, and, if applicable, study day as a continuous effect and treatment-by-study day interaction. The covariance structure to model the within-patient errors will be unstructured. If the available data cannot support the covariance structure (e.g., due to missing values), other structures will be attempted. If the unstructured covariance matrix results in a lack of convergence, the heterogeneous Toeplitz (TOEPH) covariance structure, followed by the heterogeneous autoregressive [ARH(1)] covariance structure, followed by the compound symmetry structure will be used. The first structure to yield convergence will be used for inference. The NewtonRaphson with ridging optimization technique will be used to aid with convergence. The Kenward-Roger approximation (KR2) will be used to estimate the denominator degrees of freedom and adjust standard errors. Type III tests based on the LS means will be used for the statistical comparison; the 90% CI will also be reported.

All tests of treatment effects will be conducted at a 1-sided alpha level of 0.05, unless otherwise stated. No adjustments for multiple comparisons will be made.

All computations for statistical analyses will be performed using SAS® software, Version 9.4 or later. All SAS programs used in the production of statistical summary outputs will be validated with independent programming prior to finalization. In addition, all program outputs will be independently reviewed. The validation process will be used to confirm that all data manipulations and calculations were accurately done. Upon completion of validation and quality review procedures, all documentation will be collected and filed by the project statisticians.

When implementing parametric methods of analysis, the distribution of analysis variables will be examined to determine if model assumptions are satisfied. Transformations or nonparametric methods of analysis may be added as sensitivity analyses if warranted. Whenever alternative methods of analysis are required, the description of the new method along with the rationale for its use will be documented in the Clinical Study Report (CSR).

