4.8 Patient Characteristics

Patient's baseline age, sex, race, height, body weight, body mass index, other baseline efficacy measures including NIAID ordinal assessment, FiO₂, respiratory rate, disease history, and preexisting conditions will be summarized using descriptive statistics by treatment arm, overall, and by study site (unpooled). These summaries will be based on both the Efficacy population and the Safety population. Patients who are missing measurements of the baseline variable being analyzed will not be included in the summary for that variable.

Patient height and weight will be collected prior to randomization. Both variables will be reported in metric units (height in cm and weight in kg) and will be summarized as continuous variables along with Body Mass Index (in kg/m²).

No statistical testing will be performed for comparisons of baseline characteristics.

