4.12 Efficacy Analyses

4.12.1 Primary Outcome and Methodology

The primary outcome variable will be defined as follows:

- For patients who survive through day 28, the value is the number of days free of mechanical ventilation.
- For patients who do not survive through day 28, the value is set to -1.

If a patient is discharged from the hospital before day 28, and if the patient is still alive at day 28, then days between hospital discharge and Day 28 will be considered ventilator free. A table listing the counts of patients with each number of ventilator free days, including patients with -1 values due to death, will be presented by treatment group. The statistical method for this endpoint will be based on the Wilcoxon rank-sum test using the van Elteren test adjusting for the randomization stratification factors (age group, sex, and site).

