4.12.4.1 Pulmonary Function

Pulmonary function will be reported daily as the range of average lowest value for SpO₂ and the highest value of oxygen flow-rate; the FiO₂ will be derived for non-closed systems. The midpoint of the range of average lowest SpO₂ and derived FiO₂ and respiratory rate for each day will be analyzed via MMRM and plotted over time by treatment group. Mean values will be calculated and differences in treatment effect estimates at Days 7, 14 and 28 will be analyzed.

If any subject has multiple FiO₂ records in a day, the maximum of the records of the day will be taken in the analysis; if a subject has multiple respiratory rate records in a day, the mean of the records of the day will be used in the analysis.

However, FiO₂ will only be available for analysis when the patients used the following devices during the study:

- Ventilator (FiO₂ is given directly in the CRF),
- Nasal Cannula (FiO₂ will be calculated using the table listed below),
- Venturi Mask (FiO₂ will be calculated using the table listed below).

FiO₂ (Fraction of Inspired Oxygen) information (from louisville.edu, for reference only):

For all supplemental oxygen delivery devices, the patient is not just breathing the direct oxygen, but rather is breathing a combination of room air plus the oxygen from the supplemental device. Different devices deliver to the patient more or less of a % of what is coming in from the tank.

Fraction of Inspired Oxygen (FiO₂) for a nasal cannula and a Venturi mask are given in the tables below. For other oxygen delivery systems, such as masks, tents, there is more oxygen that "blows by" or is lost, therefore higher flow rate setting on the oxygen tank are needed to achieve the same FiO₂. A tracheostomy would require different calculations as well.

Example: with a nasal cannula, we assume that the fraction of oxygen that is inspired (above the normal atmospheric level or 20%) increases by 4% for every additional liter of oxygen flow administered.

For a Nasal Cannula:

Oxygen tank FLOW RATE in liters / min	FiO₂ -- Fraction of Inspired Oxygen value
0 (no oxygen, just room air)	.20
1 L / min	.24
2 L / min	.28
3 L / min	.32
4 L / min	.36
5 L / min	.40
6 L / min	.44

For a Venturi Mask:

Oxygen tank FLOW RATE in liters / min	FiO₂ – Fraction of Inspired Oxygen Value
0 (no oxygen, just room air)	.20
4 L / min	.26
6 L / min	.31
8 L / min	.375
12 L / min	.447

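### The mixed model for SpO2, FiO2 and respiratory rate omits the baseline value of the outcome, so these exploratory comparisons lose precision that the screening data could supply

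*SAP*

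**What the plan says.** SAP 4.1 makes a mixed model for repeated measures (MMRM) the default for quantitative variables when no other method is named. It gives the terms as "The model will include treatment, age group, sex, and site as fixed categorical effects, and, if applicable, study day as a continuous effect", followed by the treatment-by-day interaction. Protocol 10.3.1 has no baseline term either ("The model will include treatment, age group, and site, and, if applicable, study day and treatment-by-study day interaction as fixed categorical effects") and leaves further detail to the SAP.

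The only efficacy outcomes expressly assigned to this model are the pulmonary measures. SAP 4.12.4.1 states: "The midpoint of the range of average lowest SpO₂ and derived FiO₂ and respiratory rate for each day will be analyzed via MMRM". The response is the daily value itself. SAP 4.1 defines change from baseline in general but does not name it as the response here. Treatment differences are then taken at Days 7, 14 and 28. Protocol 10.3.3.3 lists this among the exploratory analyses ("Pulmonary function will be analyzed via MMRM analysis"), and the SAP places it under other efficacy analyses (4.12.4).

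The main outcomes use a different method. For ventilator-free days, SAP 4.12.1 says "The statistical method for this endpoint will be based on the Wilcoxon rank-sum test using the van Elteren test". The worst NIAID score (4.12.3.2) and length of stay (4.12.3.4) also have van Elteren tests.

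The Schedule of Activities (Protocol Table 2-1) collects SpO2, oxygen flow and vital signs at screening, and its notes include respiration rate among the vital signs. SAP 4.8 describes "other baseline efficacy measures including NIAID ordinal assessment", FiO2 and respiratory rate, but only in summaries.

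**The concern.** Patients enter with very different respiratory status. Protocol 6.1 accepts infiltrates on imaging or SpO2 of 95% or less on room air. SAP 4.14 expects baseline NIAID scores of 3, 4 and 5, which run from non-invasive ventilation or high-flow oxygen to no supplemental oxygen. Randomisation is stratified by age group, sex and site, and none of these directly balances respiratory severity.

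If the model has no baseline term, the part of that spread which persists after treatment starts stays in the residual variation. A chance difference between the arms at baseline then carries into the later differences. At stake are the width of the confidence intervals and how clearly the Day 7, 14 and 28 differences can be read. The trial takes no PK or PD samples (Protocol 9.5, 9.6), so its daily respiratory measurements are worth analysing efficiently.

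**Working it through.** **Plan figures.** The documents give no precision or power figure for this model. Their 81% power with 100 per arm (Protocol 10.1, SAP 3.2) is for the primary rank test, which does not use the MMRM.

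**Inputs.** n = 100 per arm; one-sided alpha 0.05 (SAP 4.1); correlation r between baseline and the outcome on a given day, assumed to be 0.3, 0.5 or 0.7.

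**1. Precision on a single day.** Adjusting for baseline multiplies the variance of the treatment difference by 1 − r² and the interval width by √(1 − r²). An unadjusted analysis needs 100/(1 − r²) per arm to match. For an effect with 80% unadjusted power, adjusted power is Φ[(1.645 + 0.842)/√(1 − r²) − 1.645].

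| r | Variance ratio | Variance cut | Interval width cut | Unadjusted n per arm for equal precision | 80% power becomes |
|---|---|---|---|---|---|
| 0.3 | 0.91 | 9% | 5% | 110 | 83% |
| 0.5 | 0.75 | 25% | 13% | 133 | 89% |
| 0.7 | 0.51 | 49% | 29% | 196 | 97% |

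**2. Chance imbalance.** The standard error of the baseline difference is √(2/100) = 0.141 SD. An imbalance of k standard errors shifts the unadjusted difference by r × k × 0.141 outcome SD. Given that imbalance, the one-sided type I error is 1 − Φ[(1.645 − rk)/√(1 − r²)].

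| r | Shift, k = 1 | Shift, k = 1.96 | Conditional type I error, k = 1.96 |
|---|---|---|---|
| 0.3 | 0.04 SD | 0.08 SD | 13% |
| 0.5 | 0.07 SD | 0.14 SD | 22% |
| 0.7 | 0.10 SD | 0.19 SD | 35% |

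**3. Over all randomisations.** Under no effect the unadjusted statistic is rk + √(1 − r²)·e, with k and e independent standard normal. Its variance is r² + (1 − r²) = 1, so the overall error rate is the nominal 5%. A simulation of 4,000 trials gave a mean error of about zero and type I error of 4.9% to 5.5%.

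**4. Would including Day 1 as a response cure this?** The SAP does not say whether Day 1 is a response. Take its linear day and treatment-by-day terms, complete data on Days 1 to 28 and compound symmetry (one of its fallback structures). The fitted difference is then an ordinary straight line through the daily differences. The days average 14.5 and their squared deviations sum to 28 × (28² − 1)/12 = 1827. Day 1 therefore has weight 1/28 + (1 − 14.5)(7 − 14.5)/1827 = 0.036 + 0.055 = 0.091 in the fitted Day 7 value. A Day 1 imbalance of 1 leaves an expected r on each later day, so the fitted Day 7 difference carries r + (1 − r) × 0.091 = 0.36, 0.55 and 0.73 of it. With only post-baseline days modelled and no covariate, the shares are 0.30, 0.50 and 0.70. Including Day 1 does not remove the imbalance under these assumptions, because each arm keeps its own intercept.

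**The case against.** The case against is substantial, and most of it limits the point rather than removing it.

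- **Scope.** A reader might infer that every continuous efficacy outcome is affected. The documents do not support this. Ventilator-free days, worst NIAID score and length of stay have their own rank tests. NIAID means at Days 7, 14 and 28 and days of supportive care have no named method and might fall to the default model, but the durations have no baseline value to add.
- **Bias.** A reader might infer that the estimates are biased or the tests invalid. Randomisation rules that out, as step 3 shows. The inflated error rates in step 2 apply only given a particular imbalance.
- **Importance.** A reader might infer that these models are the only physiological evidence of drug effect. They are not: the COVID-19 panel (Protocol Appendix 2) is collected repeatedly, and SAP 5.1 plans a table for it.
- **Availability.** Screening SpO2 and respiration rate are scheduled for all patients, but baseline FiO2 will be incomplete. SAP 4.12.4.1 derives FiO2 only for ventilator, nasal cannula and Venturi mask, so it may be missing in the sickest patients at entry. This stands. However, baseline missingness is settled before randomisation, so a missing-baseline indicator does not bias the comparison. It only recovers less precision.
- **Timing.** SpO2 and oxygen flow are daily extremes rather than timed pre-dose readings, and screening may fall on Day 1. For respiratory rate, SAP 4.12.4.1 averages a day's records, and Day 1 vital signs are taken both before and after dosing. A baseline rule is therefore needed.
- **Size.** Every r is assumed. The formula is for one day, and the relevant correlation is the one left after age group, sex and site. The table is an upper guide.

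**Conclusion.** The point holds for the three pulmonary outcomes. The MMRM leaves out a covariate whose source data are already collected, so the differences at Days 7, 14 and 28 are less precise than they could be and chance baseline differences are not adjusted for. The gain forgone is up to about 9%, 25% or 49% of single-day variance at assumed correlations of 0.3, 0.5 or 0.7. It is smaller by Day 28 if the correlation fades, and smaller for FiO2 where the baseline is missing.

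The loss is efficiency in exploratory analyses. It is not a threat to validity: over all randomisations there is no bias and no type I error inflation. The primary analysis, the van Elteren secondary analyses and the 81% power are untouched. The change is worth making because it is cheap.

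**What to change.** In SAP 4.1 or 4.12.4.1, for SpO2, FiO2 and respiratory rate:

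- Add the last value recorded before first dose, and its interaction with study day, as covariates. Use the screening value if the Day 1 daily summary cannot be shown to be pre-dose.
- Model only post-baseline days as responses, and state which day is the first.
- For FiO2, also adjust for baseline NIAID score or use a missing-baseline indicator, so that patients on devices without a derived FiO2 are not dropped for lack of a baseline.

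The cost is one or two extra model terms and a missing-baseline rule for FiO2, with no new data collection. Protocol 10.3.1 leaves MMRM detail to the SAP and requires an amendment only for a change to a principal feature, so an SAP revision appears to be enough. It should be dated before the final unblinding. The change does not deal with FiO2 values missing by device after baseline, which is a separate matter.

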4.12.3.2 NIAID Ordinal Assessment

The NIAID will be assessed daily and defined as the lowest score achieved for that day.

The scoring is based on the clinical status of the patient as described below.

NIAID Score	Description
1	Death

2	Hospitalized, on invasive mechanical ventilation or extracorporeal membrane oxygenation (ECMO)
3	Hospitalized, on non-invasive ventilation or high flow oxygen devices
4	Hospitalized, requiring supplemental oxygen
5	Hospitalized, not requiring supplemental oxygen - requiring ongoing medical care (COVID-19 related or otherwise)
6	Hospitalized, not requiring supplemental oxygen - no longer requires ongoing medical care
7	Not hospitalized, limitation on activities and/or requiring home oxygen
8	Not hospitalized, no limitations on activities

The lowest value from Day 1 through Day 28 for a patient on the NIAID ordinal scale will be analyzed using the van Elteren test adjusting for the randomization stratification factors. The number need to treat (NNT) to prevent one patient from progressing to level 2 or 1 will be calculated. Mean values will be calculated and differences in treatment effect estimates at Days 7, 14 and 28 will be analyzed. Mean value by treatment group will be plotted over time.

[figure not shown]
Time to the first 2-point improvement on the NIAID scale will be analyzed between treatment groups. The time for subjects who did not achieve 2-point improvement will be censored at day 28 and stratification will be ignored in this analysis. A Kaplan-Meier plot with log-rank test will be used to compare treatment groups.

The stacked bar plot(s) representing the proportion of subjects in each score by treatment arm over time will be generated with stratification ignored. An example of such plot is as follows. The details of the score will be included in the footnote of the plot.

In addition to the stacked bar plot based on the original NIAID scores, another stacked bar plot that lumps NIAID scores into four categories will be generated. The four new categories are:

- a. Death (NIAID score = 1),
- b. IMV/ECMO (NIAID score = 2),
- c. Requiring O₂ or medical care (NIAID scores = 3, 4, 5), and
- d. Not requiring O₂ nor medical care (NIAID scores = 6, 7, 8).

Figure 2.0 Example of a Stacked Bar Plot:

4.12.3.3 28-day Mortality

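### The protocol treats study day as categorical in the MMRM and the SAP treats it as continuous, which puts the requested Day 7, 14 and 28 differences on one straight line

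*SAP*

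**What the plan says.** Protocol 10.3.1 describes the default model for continuous outcomes and includes, where applicable, "study day and treatment-by-study day interaction as fixed categorical effects". It leaves further detail to the SAP: "Additional details on the MMRM analyses will be described in the SAP".

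SAP 4.1 keeps the MMRM as the default for quantitative variables but specifies "study day as a continuous effect and treatment-by-study day interaction". It contains no quadratic term, spline or categorical-day alternative, and it does not explain the change. On covariance it says "The covariance structure to model the within-patient errors will be unstructured", followed by three simpler structures if the model does not converge.

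The model is applied by name in SAP 4.12.4.1, where the midpoint of the lowest-SpO2 range, derived FiO2 and respiratory rate "for each day will be analyzed via MMRM and plotted over time by treatment group". The same section adds that "differences in treatment effect estimates at Days 7, 14 and 28 will be analyzed".

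SAP 4.12.3.2 makes the matching request for the NIAID score, "Mean values will be calculated and differences in treatment effect estimates at Days 7, 14 and 28 will be analyzed", without naming a model.

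**The concern.** The protocol model gives every study day its own treatment difference. The SAP model allows only an intercept difference and a slope difference between arms. A request for effects at three named days suggests that each will be estimated for that day, and the SAP model cannot do this: records from all other days, through the straight-line assumption, determine what is reported at Days 7, 14 and 28.

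A difference that is not linear in time is plausible here. The illness is acute, follow-up covers 28 days, and dosing is on Days 1 and 15. If the difference is curved, a mid-course benefit can be shrunk, and a difference can be reported on a day when none exists. The change also reverses a model term that the protocol had already fixed, which goes further than supplying additional detail.

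**Working it through.** **1. The constraint.** The coding comes from Protocol 10.3.1 and SAP 4.1; the contrast days come from SAP 4.12.4.1 and 4.12.3.2. With continuous day and a treatment-by-day interaction, the modelled difference is D(t) = a + b·t. Since (14 − 7)/(28 − 7) = 1/3,

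D(14) = D(7) + (1/3)·[D(28) − D(7)]

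for any data set. Three contrasts come from two parameters. With categorical day there is no such restriction, and with complete data the expected contrast on each day equals the true difference.

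**2. Size under assumed shapes.** The documents give no figure to reproduce and no shape for the difference, so the shapes below are assumptions. Each curved shape has a maximum of 1.0 in arbitrary units. A least-squares line was fitted to the 28 daily differences with equal weights and complete data; a compound-symmetry covariance gives the same line.

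One row by hand, the plateau min(t/7, 1):
- The shortfall from 1 on Days 1 to 6 is 6/7, 5/7, …, 1/7, with sum 3. The mean is (28 − 3)/28 = 0.893.
- The mean day is 14.5, and Σ(t − 14.5)² = 28·(28² − 1)/12 = 1827.
- The shortfall-weighted sum of days is 56/7 = 8. The cross-product is 14.5·3 − 8 = 35.5, and the slope is 35.5/1827 = 0.0194.
- The fitted values are 0.893 − 7.5·0.0194 = 0.75 at Day 7, 0.893 − 0.5·0.0194 = 0.88 at Day 14, and 0.893 + 13.5·0.0194 = 1.16 at Day 28.

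| Assumed true difference | Day 7 true → fitted | Day 14 true → fitted | Day 28 true → fitted |
|---|---|---|---|
| Constant at 1 | 1.00 → 1.00 | 1.00 → 1.00 | 1.00 → 1.00 |
| Linear, (t − 1)/27 | 0.22 → 0.22 | 0.48 → 0.48 | 1.00 → 1.00 |
| Half-sine hump, sin(πt/28) | 0.71 → 0.67 | 1.00 → 0.64 | 0.00 → 0.57 |
| Ramp from Day 15 to Day 20, then 1 | 0.00 → 0.01 | 0.00 → 0.37 | 1.00 → 1.08 |
| Plateau, min(t/7, 1) | 1.00 → 0.75 | 1.00 → 0.88 | 1.00 → 1.16 |
| Peak at Day 7, back to 0 at Day 28 | 1.00 → 0.62 | 0.67 → 0.49 | 0.00 → 0.23 |

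The largest absolute errors in the table are 0.38 at Day 7, 0.37 at Day 14 and 0.57 at Day 28. Several entries are close to zero.

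**3. Sensitivity to these assumptions.** A triangular hump peaking at Day 14 gives 0.50 there in place of 1.00. Serial correlation changes the weights: for the Day 7 peak, an AR(1) covariance gives a fitted Day 7 value of 0.44 (correlation 0.8) or 0.22 (correlation 0.95), compared with 0.62 above. The constant and linear rows stay unbiased under every covariance tried.

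**4. Model size.** Over 28 daily levels, study day and its interaction use 27 + 27 = 54 parameters when categorical and 2 when continuous. An unstructured covariance has 28·29/2 = 406 parameters under either coding.

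**The case against.** **The bias is not established.** A reader might infer that the three differences will come out wrong. The documents do not support that. If the true difference is constant or linear in day, the SAP model is unbiased and usually more precise. Nor does a course of worsening and recovery in each arm make the difference between arms curved, because two curved trajectories can differ by a constant. This objection stands, so the point is conditional on shape.

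**The reach is narrow.** Only pulmonary function names the MMRM; it is exploratory in the protocol and listed under other efficacy in the SAP. Protocol 10.3.3.2 assigns the NIAID scale to the Wilcoxon test. SAP 4.12.3.2 names no model for the mean-score contrasts, so they are reached only if the SAP 4.1 default is read to cover an ordinal score. This also stands.

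**There are partial safeguards.** Daily means are to be plotted, so curvature would be visible beside the model estimates. SAP 4.1 allows transformations or nonparametric methods as sensitivity analyses, but the check that leads to them concerns distributions, not the time course. Protocol 10.3.1 delegates detail to the SAP and requires an amendment only for a principal feature; other changes are to be justified in the study report. That may make the change permissible, but it does not give the reason for it.

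**The absent baseline value is not part of the conflict.** Neither model adjusts for the baseline value of the outcome. In a randomized comparison this costs precision and does not create bias.

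**Conclusion.** The two documents specify different models, and the SAP's choice makes the Day 7, 14 and 28 differences points on one line. That much follows from the text and algebra alone. Whether the reported values are biased depends on the true difference. The bias is zero if the difference is constant or linear in day. For the curved shapes in the table, errors run from near 0 to about 0.4 at Days 7 and 14 and about 0.6 at Day 28, relative to a maximum of 1.0. Those sizes rest on assumed shapes, equal weights and complete daily data. They illustrate the risk and do not estimate the error in this trial; sharper peaks or strong serial correlation can give larger values.

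The affected analyses are SpO2, FiO2 and respiratory rate, and possibly the NIAID mean score. The primary ventilator-free-days analysis and the other van Elteren, chi-square and log-rank analyses have no study-day term and are untouched. The inconsistency should be corrected, but it does not threaten the trial's main conclusion.

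**What to change.** - In SAP 4.1, restore study day and treatment-by-study-day as categorical effects, as in the protocol, and take the Day 7, 14 and 28 contrasts from that model.
- If 28 daily levels do not converge, use the covariance fallbacks already in SAP 4.1, or a reduced set of days such as 2, 7, 14, 21 and 28.
- State in SAP 4.12.3.2 which model gives the NIAID contrasts.
- Optionally, add the baseline value of the outcome as a covariate for precision.

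If the sponsor prefers continuous day, the minimum is a stated justification and a categorical-day or non-linear sensitivity analysis.

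The change takes a sentence or two in the SAP and a small change in the program. The price is 54 study-day parameters in place of 2 over 28 daily levels, with somewhat wider intervals; with the reduced set, daily records are left out of the model. Neither coding supplies the SpO2 values that are not collected after discharge, so Day 28 pulmonary estimates will need cautious reading either way.
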